4.3 Effectiveness Analyses

The primary effectiveness endpoint is technical success, defined by $\leq 50\%$ diameter stenosis after atherectomy with the Revolution™ Peripheral Atherectomy System, prior to adjunctive therapy, as measured by the independent core laboratory on the post-atherectomy contrast angiogram. Effectiveness will be assessed for all investigator-identified target lesions in the PP analytic group and will be calculated on per-lesion basis.

$H_0: P_E \leq PG_E$ versus $H_A: P_E > PG_E$

Where P_E is the proportion of subjects with technical success, as defined by angiographically-determined $\leq 50\%$ target lesion diameter reduction on the post-

atherectomy core laboratory measurement⁵. The effectiveness performance goal, PG_E, is technical success defined in the same manner, derived from the published literature.

The primary effectiveness endpoint will be calculated for those PP target lesions that fall at or below the specified acceptable reference vessel diameter of 4.0 mm, as determined by the core laboratory. Target vessels with diameters < 2.0 mm and > 4.0 mm will be excluded from the analysis, since even the largest bit size (2mm) would not result in a post-atherectomy channel size of $\geq 50\%$ RVD. For subjects with >1 lesion, it is possible that one vessel qualifies for the PP analysis with RVD ≤ 4.0 mm and others do not, with RVD >4.0 mm. For lesion level effectiveness endpoints, only PP qualifying lesions will be included in the analysis. For subject level effectiveness endpoints, subjects with nonqualifying PP lesion(s) will be excluded from the analysis.

It was originally planned for the primary effectiveness endpoint analysis to use the E+M approach for one sample correlated binary data with cluster size of one or two that accounts for correlations between multiple target lesions within the same subject⁵. However, based on a recommendation from FDA the primary analysis method was changed to generalized estimating equations (GEE). FDA also recommended assessing the power of this analysis using this method, however, it was determined that information needed for the assumptions required was not available, e.g. the correlation between lesions within a subject.

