6.5. Study Populations

The point of enrollment in this study occurs when a study device first enters a subject's vasculature.^e The following populations will be analyzed in the study:

Intention to treat (ITT) analysis: The ITT analysis will be performed on all enrolled subjects in whom the study device entered the vasculature, irrespective of adherence with the entry criteria, treatment actually received, subsequent withdrawal, or deviation from the investigational plan.²⁴

Per Protocol analysis: The PP analysis will be performed on target lesions with core laboratory-determined RVD falling within the pre-specified anatomic eligibility criteria of ≤ 4.0 mm. The effectiveness endpoints will be determined using the PP analytic subset to exclude lesions where the largest bore (2.0 mm) study device is less than 50% of the RVD (see Section 7.3, page 22, below).^f

^e This point is defined as entry of the study device into the access sheath/guide at the level where the sheath/guide enters the subject's body.

^f Use of the 2.0 mm bore in a vessel larger than 4.0 mm in diameter would not result in a lumen channel that exceeds 50% of the RVD. In other words, the residual stenosis after successful atherectomy would still not meet the criteria

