7.3. Primary Effectiveness Endpoint

The primary effectiveness endpoint is technical success, defined by $\leq 50\%$ diameter stenosis after atherectomy with the Revolution™ Peripheral Atherectomy System, prior to adjunctive therapy, as measured by the independent core laboratory on the post-atherectomy contrast angiogram. Effectiveness will be assessed for all investigator-identified target lesions in the PP analytic group and will be calculated on a per-lesion basis.

$$H_0: P_E \leq PG_E \text{ versus } H_A: P_E > PG_E$$

for technical success; even though the device performed as designed. Since the eligibility criteria are site-determined, the subject may still be included in the ITT population but the lesion would be excluded from the PP analytic group.

where P_E is the proportion of lesions with technical success, as defined by angiographically-determined $\leq 50\%$ target lesion diameter reduction on the post-atherectomy core laboratory measurement.^g The effectiveness performance goal, PGE, is technical success defined in the same manner, derived from the published literature.

The primary effectiveness endpoint will be calculated for those target lesions that fall at or below the specified acceptable reference vessel diameter of 4.0 mm, as determined by the core laboratory. Target vessels with diameters > 4.0 mm will be excluded from the analysis, since even the largest bit size (2 mm) would not result in a post-atherectomy channel size of $\geq 50\%$ RVD.

The primary effectiveness endpoint analysis will use the E+M approach for one sample correlated binary data with cluster size of one or two that accounts for correlations between multiple target lesions within the same subject.^h

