2.1 Secondary Endpoints

Secondary endpoints will consist of the following with level of analysis in parentheses:

- 1) Change in percent stenosis after treatment with RevolutionTM Peripheral Atherectomy System, determined after atherectomy and prior to other adjunctive therapies, as measured by the angiographic core laboratory (lesion level);
- 2) Procedural success as defined by target lesion residual stenosis of $<30\%$ at the conclusion of the index procedure, after atherectomy and any adjunctive endovascular treatment, as measured by the angiographic core laboratory (lesion level);
- 3) Assessment of the individual components of the primary safety endpoint (MAE); including all-cause mortality, major target limb amputation, clinically significant distal embolization, major target vessel perforation requiring surgical or endovascular repair, and clinically-driven TLR, measure through 30 days and at 6 months (subject level);
- 4) Minor unplanned target limb amputation rate through 30 days and 6 months (subject level);
- 5) Myocardial infarction through 30 days and 6 months (subject level);

³ The shoulder-to-shoulder length is determined visually using a Quantitative Vascular Angiography (QVA) software application. RVD is determined at the location of the MLD, linearly interpolated between the luminal diameters just proximal to and distal to each shoulder.

- 6) Incidence of target vessel revascularization (TVR) through 30 days and 6 months (subject level);
- 7) Frequency of angiographic procedural distal embolization (symptomatic) in the target limb as confirmed angiographically by the core laboratory (subject level);
- 8) Primary patency of the target lesion at 30 days and 6 months, determined by duplex ultrasound or angiography (subject level);
- 9) Primary-assisted patency of the target lesion at 30 days and 6 months, determined by duplex ultrasound or angiography (subject level);
- 10) Secondary patency of the target lesion at 30 days and 6 months, determined by duplex ultrasound or angiography (subject level).

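### SAP 4.3 drops the whole subject from the patency endpoints when one target lesion falls outside the diameter limits, although the per-protocol set is defined by lesion

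*SAP*

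**What the plan says.** SAP 4.3 foresees subjects whose lesions fall on both sides of the limit: "For subjects with >1 lesion, it is possible that one vessel qualifies for the PP analysis with RVD" at or below 4.0 mm while another lies above it. It then sets two rules:

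- Lesion level: "For lesion level effectiveness endpoints, only PP qualifying lesions will be included in the analysis".
- Subject level: "subjects with nonqualifying PP lesion(s) will be excluded from the analysis".

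The SAP's list of secondary endpoints gives the level of each. It includes "Primary patency of the target lesion at 30 days and 6 months, determined by duplex ultrasound or angiography (subject level"), and primary-assisted and secondary patency carry the same label. SAP 5.2 classes patency as effectiveness. Technical success, change in stenosis and procedural success are lesion level.

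The Protocol works by lesion throughout. Section 6.5 describes the PP set as target lesions with a core-laboratory reference vessel diameter (RVD) of at most 4.0 mm, and SAP 3.2 repeats this. Footnote f to Section 6.5, which runs on into Section 7.3, says that in such a case "the subject may still be included in the ITT population but the lesion would be excluded from the PP analytic group".

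SAP 4.3 gives one reason for the diameter limit, attached to the primary endpoint: "since even the largest bit size (2mm) would not result in a post-atherectomy channel size of" at least 50% of RVD. Protocol footnote f ties the same reason to technical success, because "the residual stenosis after successful atherectomy would still not meet the criteria". The subject-level rule has no reason of its own.

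**The concern.** The step from lesion to subject appears only in SAP 4.3. A subject with one lesion at 3.5 mm and another read by the core laboratory at 4.2 mm keeps the first lesion for technical success but loses it for all three patency endpoints at both time points.

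Two things follow. Usable data on lesions within the limits are discarded. Exclusion also depends on how many lesions a subject has, because each further lesion is another chance to be removed. The patency results then describe a group with fewer multi-lesion subjects than were enrolled.

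No other planned analysis recovers these subjects. SAP 3.1 assigns the ITT population to safety outcomes, and neither document specifies patency on all enrolled subjects. The subjects concerned are validly enrolled: Protocol 9.3 bases eligibility on site measurements and does not treat core-laboratory values as deviations.

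**Working it through.** **Inputs from the documents.** 121 subjects and 1.5 target lesions per subject (SAP 3.3). The plan's own conversion reproduces: 165 lesions / 1.5 = 110 subjects. The plan gives no figure for subjects with mixed lesions.

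**Assumptions.** q is the share of lesions that are nonqualifying; it is not in the documents, so a range is shown. Half the subjects have one lesion and half have two, which matches 1.5. The two lesions of a subject are independent at first, then have correlation r = 0.5.

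**Formulas, per enrolled subject.**

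- Mixed (one qualifying, one not): M = 0.5 × 2q(1−q)(1−r)
- At least one qualifying lesion: A = 0.5(1−q) + 0.5[1 − q² − r·q(1−q)]
- Share of subjects with a qualifying lesion who are discarded: M/A
- Subjects kept under SAP 4.3: 121(A−M); kept if only lesions are dropped: 121·A

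**Example, q = 10%, r = 0.** M = 0.5 × 2 × 0.10 × 0.90 = 0.090. A = 0.45 + 0.495 = 0.945. M/A = 9.5%. Of 121 subjects, about 10.9 are mixed; 114.3 have a qualifying lesion and 103.5 are kept by the SAP.

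| q | M/A, r = 0 | Kept, SAP rule | Kept, lesion-only rule | Qualifying lesions lost, M/[1.5(1−q)] | M/A, r = 0.5 |
|---|---|---|---|---|---|
| 5% | 4.9% | 112.1 | 117.8 | 3.3% | 2.5% |
| 10% | 9.5% | 103.5 | 114.3 | 6.7% | 4.9% |
| 20% | 18.2% | 87.1 | 106.5 | 13.3% | 9.5% |

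The kept and lost columns are for r = 0 and before any missing imaging. For r = 0.5 at q = 10%: M = 0.045, A = 0.45 + 0.5(1 − 0.01 − 0.045) = 0.9225, and M/A = 4.9%.

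**Dependence on lesion count, q = 10%.** A one-lesion subject is removed with probability 10%. A two-lesion subject is removed with probability 1 − 0.9² = 19% if r = 0, or 1 − (0.81 + 0.045) = 14.5% if r = 0.5.

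**Precision.** At an assumed patency of 80%, the 95% half-width is 1.96·√(0.16/n). At q = 10%, r = 0, it is 7.7 points under the SAP rule (n = 103.5) and 7.3 under the lesion-only rule (n = 114.3). At q = 20% it is 8.4 against 7.6.

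**The case against.** The best case for the SAP rule is that it is pre-specified and has a plausible purpose, though an unstated one. Patency is one result per subject, and its algorithm uses events that are not tied to a particular lesion. Under SAP 5.21, imaging after any target vessel revascularization (TVR) is censored, a clinically driven target lesion revascularization (TLR) sets failure, and failure carries forward. In a mixed subject, an intervention on the nonqualifying lesion could censor or fail the qualifying one. Removing the subject avoids that. This part stands, and it means that simply switching to qualifying lesions is not enough: the SAP must also attribute events to lesions. It does not require discarding the qualifying lesion.

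The reach is also narrow. Patency has no performance goal and no test, and the success criteria in SAP 4.5 rest on the two primary endpoints. This stands in full.

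The size is uncertain too. Site eligibility already caps RVD at 4.0 mm, so oversized lesions should arise mainly where site and core laboratory disagree. All target lesions lie in one limb, so independence may overstate the mixing. Both points stand, hence the range and the correlated case.

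A reader might infer that the bit-size reason has nothing to do with patency. The documents do not support that. SAP 5.2 counts stenosis of 50% or more as loss of patency, so an oversized lesion treated by atherectomy alone could start near failure. Protocol 6.5 also assigns effectiveness endpoints generally to the PP set. That supports leaving out the oversized lesion, not the same subject's qualifying lesion.

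**Conclusion.** The point holds for primary, primary-assisted and secondary patency. SAP 4.3 excludes by subject where the Protocol and SAP 3.2 exclude by lesion, and gives no reason for the difference. The loss is about 5% to 18% of subjects with a qualifying lesion for q from 5% to 20%, given an even split of one- and two-lesion subjects and independent lesions. It is about half that with a within-subject correlation of 0.5. Both q and the spread of lesions per subject are assumed.

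The higher removal rate for multi-lesion subjects follows from the rule itself unless a subject's lesions always qualify or fail together. A reader might go further and infer that reported patency will be too favorable, or that study success is at risk. Neither follows: the documents do not say how patency varies with lesion count, so the direction of bias cannot be derived, and no primary endpoint is touched. The cost in precision is modest. This is a correction worth making to the secondary analyses.

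**What to change.** In SAP 4.3, replace the subject-level sentence with rules that cover four things:

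1. **Inclusion.** Determine subject-level patency from the subject's qualifying PP lesions. Exclude a subject only if no lesion qualifies.
2. **Combination.** State how several lesions give one subject result, which the SAP does not do at present. For example, any failed qualifying lesion fails the subject.
3. **Attribution.** State in SAP 5.21 to 5.23 that TLR or TVR confined to a nonqualifying lesion or its vessel neither sets failure for the qualifying lesion nor censors its imaging.
4. **Support.** Report the same patency table for all enrolled subjects and all target lesions.

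Reconcile the diameter limits in the same edit. SAP 4.3 also excludes vessels below 2.0 mm, but SAP 3.2 and Protocol 7.3 set no lower limit for this analysis, and the bit-size reason does not explain one. Until this is settled, the meaning of nonqualifying is itself unclear.

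The cost is a few SAP sentences, lesion-level attribution of revascularizations and some programming. No new imaging or visits are needed.

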4.4 Safety Analyses

The primary safety endpoint for this study is a composite endpoint of any MAE through 30 days, as adjudicated by the CEC. MAE is defined as 30-day all-cause mortality, clinically-driven TLR, major target limb amputation, major target vessel perforation requiring surgical or endovascular repair and clinically-significant distal embolization in the target limb. The rate of MAE will be compared to a performance goal with the following null and alternative hypotheses:

$$H_0: P_S \leq P_{GS} \text{ versus } H_A: P_S > P_{GS}$$

where P_S is the proportion of subjects free from MAE through 30 days and P_{GS} is the safety performance goal derived from the studies reporting the elements contained in the composite MAE endpoint.

The Exact binomial one-sided 97.5% confidence interval will be used to test the primary safety endpoint.

⁵ Technical success is defined on the post-atherectomy angiogram, prior to adjunctive therapy with balloon angioplasty, stent deployment, or any other intervention.

4.5 Study Success Criteria

The study will be considered a success if both the primary endpoints meet their respective Performance Goals. For the effectiveness endpoint, this translates into observing a one-sided 97.5% lower confidence limit (LCL) of the point estimate above 76% and for the safety endpoint it means observing a one-sided 97.5% LCL above 80%.

4.6 Additional Analyses

4.61 Demographics and Baseline Characteristics

The baseline demographics and anatomic characteristics of the treatment group will be presented with descriptive statistics.

4.62 Changes to Planned Analyses

All analyses will be detailed in the Statistical Analysis Plan (SAP). Any changes to the planned analyses will be documented as amendments to the SAP and in the study report.

4.63 Interim Analyses

The Data Safety Monitoring Board (DSMB) will review safety data (including components of the primary effectiveness endpoint, since these may impact safety) to ensure that it is ethical to continue the study based on the absence of unacceptable risks to the subject.

There will be a descriptive safety and effectiveness analysis of the primary endpoints after 25 subjects have reached the 30 days Follow-Up milestone by independent statisticians. Enrollment will not stop during this analysis. The results of this analysis will not be made public before the formal primary endpoint analysis and may be used for regulatory submission(s) outside of the US.

4.64 Subgroup Analyses

Subgroup analyses will be performed on target lesions of the superficial femoral, popliteal and tibial arteries. Additional subgroup analyses are planned for gender, diabetes mellitus, Rutherford Class, Age 75 years cutoff, lesion length tercile, and chronic total occlusion. The analyses will comprise descriptive analyses of the primary and secondary effectiveness endpoints.

4.65 Univariate/Multivariate Analyses

Univariate and multivariate predictor analyses will be carried out on the primary endpoints using logistic regression.

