2. ENDPOINT DEFINITIONS

2.1 Primary Safety Endpoint

The primary safety endpoint is a composite endpoint triggered by the occurrence of any five categories of events through 30 days after the index procedure¹. These events are the following:

1. All-cause mortality- Death from any cause, from the point of enrollment through 30 days.
2. Clinically-driven TLR- Any revascularization of the target lesion that occurs after the subject has left the procedure room following the index procedure. TLR do not include adjunctive interventions performed during the index procedure, whether planned or for failed atherectomy or for complications of atherectomy. TLRs are considered to be clinically-driven when they occur as a result of restenosis >50% diameter reduction as measured angiographically or by duplex ultrasound (occlusion or stenosis with Peak Systolic Velocity Ratio >2.4)².
3. Perforation of the target vessel- Imaging evidence (standard contrast angiography, computed tomography angiography or open surgical/pathology visualization) of target vessel perforation from any cause. For angiography and CTA, perforation is defined by contrast extravasation outside of the adventitia.
4. Clinically- significant distal embolization- Target limb embolization documented on core laboratory- assessed angiography or with open surgery/pathology, accompanied by symptoms referable to the involved vascular bed.
5. Major amputation- Amputation of the target limb that results in limb shortening; i.e. is performed at or above the level of the malleoli.

The composite endpoint and each individual component are all subject level endpoints.

¹ The index procedure is considered to occur on day 0; the first post-procedure day is day 1, and so on. The 30-day time point includes any events with a start date prior to 11:59PM on day 30.

² If an angiogram and a duplex ultrasound imaging study are discordant within any 30-day period, the angiographic results will supersede the duplex findings.

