2.2 Primary Effectiveness Endpoint

The primary effectiveness endpoint is technical success defined as acute debulking resulting in a reduction of stenosis to $\leq 50\%$ after treatment with RevolutionTM Peripheral Atherectomy System from baseline and prior to other adjunctive therapies at the conclusion of the index procedure, as measured by angiographic core laboratory.

Within any target lesion, stenosis is measured at the point of the minimum luminal diameter (MLD) over its shoulder -to – shoulder length³. The reference vessel diameter (RVD) is the interpolated diameter from the point just proximal to the point just distal to the target lesion. The percent stenosis is calculated as:

$$\% \text{ Diameter Stenosis} = 1 - \text{MLD}/\text{RVD}.$$

This is a lesion level endpoint.

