Poolability analysis will also be performed on the primary endpoints comparing across sites after adjusting for covariates difference. Logistic regression models will be utilized to include unbalanced covariates and site as an independent variable and the study outcome as dependent variable to assess outcome difference. If the p-value of site effect is less than 0.10, further analyses will be undertaken to investigate the imbalance of the study outcome.

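### The logistic models for technical success in SAP 4.65 and 4.2 name no method for within-subject correlation, although SAP 4.3 adopts GEE for the same lesion-level outcome

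*SAP*

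**What the plan says.** The two primary endpoints have different units. For technical success, SAP 2.2 states: "This is a lesion level endpoint". For safety, SAP 2.1 states: "The composite endpoint and each individual component are all subject level endpoints".

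For the primary effectiveness test, SAP 4.3 first describes a method that "accounts for correlations between multiple target lesions within the same subject", then records a change to GEE on FDA's recommendation. It adds that the correlation between lesions of one subject is not known. That change is written for the primary effectiveness analysis only.

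Two other places model the same outcome:

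- SAP 4.65 (predictors): "Univariate and multivariate predictor analyses will be carried out on the primary endpoints using logistic regression". It lists no predictors and gives no decision rule.
- SAP 4.2 (poolability): "Logistic regression models will be utilized to include unbalanced covariates and site as an independent variable and the study outcome as dependent variable". It continues: "If the p-value of site effect is less than 0.10, further analyses will be undertaken". Protocol 7.14 is the same in substance.

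Neither place mentions GEE, a random effect or a clustered variance, and neither separates the lesion-level endpoint from the subject-level one.

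**The concern.** An analyst who follows 4.65 and 4.2 literally would fit standard logistic regression to about 165 lesion rows as if they came from 165 independent units. SAP 4.3 has already accepted that they do not.

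The choice matters most for covariates that are constant within a subject. All 13 covariates listed in SAP 4.2 are of this kind. Rutherford category and ABI/TBI describe a limb, but all target lesions must lie in one limb. Site is also constant within a subject. For these terms, positive correlation means that the lesions carry less information than their number suggests. Intervals are then too narrow, and chance predictors or chance site differences are reported too often. The supporting analyses would also rest on a different error model from the primary analysis of the same data.

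**Working it through.** **Inputs from the documents.** 110 subjects, 165 lesions, success 86% against a goal of 76%, one-sided 0.025, 90% power, 1.5 lesions per subject (SAP 3.3, Table 2); site trigger p < 0.10 (SAP 4.2).

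**Assumed inputs.** Within-subject correlation (ICC) of 0.1, 0.3 and 0.5. Lesion split of 55 subjects with one lesion and 55 with two, so (55×1 + 55×2)/110 = 1.5. As a more uneven alternative, 75, 20, 10 and 5 subjects with one, two, three and four lesions (also 165 lesions). 6 or 11 sites after pooling of small sites.

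**1. The plan's own figure.** The documents give no figure for these models. The only stated figure that uses the lesion as unit is the sample size:

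n = [(1.960×√(0.76×0.24) + 1.282×√(0.86×0.14)) / 0.10]² = [(0.8371 + 0.4447)/0.10]² = 164.3, so 165.

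The 165 reproduces, and the formula treats lesions as independent.

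**2. Design effect for a subject-level term.** DE = 1 + (Σm²/Σm − 1)×ICC, where m is the number of lesions in a subject. The unclustered standard error is 1/√DE of the correct one.

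- Even split: Σm²/Σm = (55 + 220)/165 = 1.667. DE = 1.07, 1.20 and 1.33; ratio 0.97, 0.91 and 0.87.
- Uneven split: Σm²/Σm = (75 + 80 + 90 + 80)/165 = 1.970. DE = 1.10, 1.29 and 1.49; ratio 0.95, 0.88 and 0.82.

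The understatement is therefore about 3% to 18% over this range.

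**3. False-positive rate for one null predictor.** Beta-binomial simulation, even split, 86% success, nominal two-sided 5%, 4,000 runs per case. "Clustered" is independence GEE with a sandwich variance.

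| ICC | Subject-level, unclustered | Subject-level, clustered | Differs within subject, unclustered | Independent per lesion, unclustered |
|---|---|---|---|---|
| 0 | 3.9% | 4.2% | 4.0% | 4.2% |
| 0.1 | 5.5% | 5.1% | 4.4% | 4.1% |
| 0.3 | 6.6% | 5.0% | 2.8% | 4.1% |
| 0.5 | 7.9% | 5.4% | 1.4% | 4.6% |

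Two further sets of runs of the unclustered subject-level case gave 4.9%, 6.7%, 8.4% and 4.7%, 6.2%, 8.1% at ICC 0.1, 0.3 and 0.5. Monte Carlo error with 4,000 runs is about √(0.05×0.95/4000) = 0.3 points.

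The unclustered standard error divided by the true standard deviation, at ICC 0.1, 0.3 and 0.5, is:

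- subject-level predictor: 0.94, 0.89 and 0.84;
- predictor that differs between a subject's lesions: 0.99, 1.06 and 1.19;
- predictor assigned independently per lesion: 0.97, 0.99 and 0.97.

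**4. Site test at nominal 10%, no true site effect, clustering ignored.** The SAP does not name the test, and the result depends on it.

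- Pearson chi-square on lesions, ICC 0, 0.1, 0.3, 0.5: 9%, 12%, 16%, 22% with 6 sites; 10%, 13%, 20%, 28% with 11.
- Likelihood ratio, from ICC 0 to 0.5: 13% rising to 28% with 6 sites; 18% rising to 42% with 11. The excess at ICC 0 is sparse-data error, not clustering.
- Wald, in data sets where every site term can be estimated, ICC 0, 0.1, 0.3, 0.5: 3.3%, 4.4%, 6.1%, 9.6% with 6 sites; at most 2.1% with 11.

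At least one site had no failures in 72% to 85% of data sets with 11 sites, and in 9% to 17% with 6. That site's log-odds is then infinite, and a robust Wald test from a GEE with one term per site is undefined.

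**The case against.** The strongest reply is that the SAP nowhere says that lesions will be treated as independent. A binary GEE with a logit link is itself a form of logistic regression, 4.3 already names GEE for technical success, and the same sentences also serve the subject-level safety endpoint, for which standard logistic regression is right. This is fair: the independence assumption follows from applying the text literally and is not stated in it. But 4.3 confines GEE to the primary analysis, so the literal application is the natural one and a clustered method should be named.

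A reader might infer that all standard errors in these models are too small. The calculations do not support that. For predictors that vary between lesions of one subject the errors can be about right or too large. Artery, lesion length and chronic total occlusion are possible examples, although SAP 4.64 names them only for descriptive subgroups.

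It is also true that the inflation rests on a correlation the SAP says is unavailable, that it is negligible at 0.1, and that a Wald site test did not exceed its nominal level. With the Wald test, sparse data offset the effect of clustering; its rejection rate with 6 sites still rises with the correlation.

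Finally, nothing decisive hangs on these models. SAP 4.2 says that its baseline comparisons are no barrier to pooling, a low site p-value only prompts more analysis, and 4.65 has no threshold. That stands, and it limits the weight of the point.

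**Conclusion.** The point holds, as a minor one. SAP 4.65 and 4.2 give plain logistic regression for a lesion-level outcome that SAP 4.3 treats as correlated. If the correlation is positive, subject-level predictors have a false-positive rate of about 5%, 6–7% and 8% at nominal 5% for an ICC of 0.1, 0.3 and 0.5. Clustered errors hold it at about 4% to 5.4%. The site test can be inflated more, to between 22% and 42% at nominal 10% and ICC 0.5 for chi-square or likelihood-ratio tests, but not for the Wald test.

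These sizes rest on the assumed ICC range, the assumed split of lesions over subjects and the assumed number of pooled sites.

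A reader might also infer that the effectiveness result or study success is compromised. It is not: SAP 4.5 depends only on the two primary confidence limits, and the effectiveness analysis already uses GEE. The models for the safety endpoint are unaffected.

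**What to change.** In SAP 4.65, and for covariate effects in SAP 4.2, state that models for technical success are logistic GEE clustered on subject with robust standard errors, as in 4.3. State that ordinary logistic regression is kept for the subject-level safety endpoint.

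For the site effect in 4.2, name a test that respects subject clustering and can still be computed when a site has no failures. One option is a permutation test that reassigns whole subjects to sites. If unbalanced covariates stay in the model, the permutation scheme must allow for them. Another option is a random site effect, with a subject effect nested in it. Neither was simulated here. A robust Wald GEE test with one term per site should not be the only test named.

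The cost is a short addition to the SAP: no new data, and standard software. Intervals for subject-level predictors become slightly wider. The site test needs somewhat more thought than a change of model name.
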